5.4.1.1.15. Virologic Breakthrough

HBV virological breakthrough is defined as having a confirmed on-treatment HBV DNA increase by $>1 \log_{10}$ from nadir level (lowest level reached during treatment) in participants who didn't have on-treatment HBV DNA level below the lower limit of quantification (LLOQ) or a confirmed on-treatment HBV DNA level >200 IU/mL in participants who had on-treatment HBV DNA level below the lower limit of quantification (LLOQ). Confirmed HBV DNA increase/level means that the criterion should be fulfilled at 2 or more consecutive time points or at the last observed on-treatment time point. On-treatment will be defined as the time period in which the participant receives any of the study interventions (including NA).

In addition, participants who experience a virologic breakthrough followed by on-treatment biochemical flare will be evaluated.

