JNJ-56136379 (JNJ-6379) is an orally administered Class N capsid assembly modulator (CAM-N) interfering with the capsid assembly and disassembly during HBV replication. JNJ-6379 binds to hepatitis B core protein (HBc) and interferes with the viral capsid assembly process, thereby preventing the polymerase-bound pgRNA encapsidation. This results in the formation of HBV capsids with normal shape but which are devoid of HBV DNA or RNA (non-functional capsids; Class N), and ultimately in the inhibition of HBV replication. In addition, JNJ-6379 also acts at an early stage of the viral life cycle by inhibiting the de novo formation of cccDNA potentially by interfering with the capsid disassembly process. JNJ-6379 was initially part of the study intervention for participants enrolled before Protocol Amendment 3 was in effect, but has been removed as study intervention with the implementation of an urgent safety measure, as described in Protocol Amendment 3.

As of Protocol Amendment 3: The term “study intervention” throughout the protocol, refers to JNJ-3989, NA, and pegylated interferon alpha-2a (PegIFN- α 2a).

OBJECTIVES AND ENDPOINTS

Below is the list of objectives and endpoints that will be evaluated in this study, delineating the details in alignment with the general objectives listed in the Master Protocol PLATFORMPAHPB2001. The details specific for this ISA are highlighted (colored fill).

Objectives	Endpoints
Primary	

 To evaluate the efficacy in terms of HBsAg levels of the study intervention (ie, JNJ-3989 + JNJ-6379^d + NA and PegIFN-α2a). 	
 Proportion of participants with a reduction of at least 2 log₁₀ IU/mL in HBsAg levels from baseline to Week 24 (end of study intervention [EOSI]).
Secondary	

 To evaluate the safety and tolerability of the study intervention. 	
 Safety and tolerability including but not limited to the proportion of participants with (serious) adverse events ([S]AEs) and abnormalities in clinical laboratory tests (including hematology,

Objectives	Endpoints
	blood biochemistry, blood coagulation, urinalysis, urine chemistry, renal biomarkers), 12-lead electrocardiograms (ECGs), vital signs, and ophthalmic and physical examinations throughout the study.

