6.7.1. NA Re-treatment Criteria and Monitoring After Stopping of NA

Participants who meet the protocol-defined NA treatment completion criteria outlined in Section 6.6, Study Intervention Completion at Week 24, will be monitored closely during the FU Period.

After stopping NA treatment, participants should be monitored as follows:

- Regular monitoring visits will be every 4 weeks during the follow-up phase in accordance with the [Schedule of Activities](#).
- A post-treatment HBV DNA value of >20,000 IU/mL should trigger re-testing of ALT/AST, HBV DNA, and total and direct bilirubin within a maximum of 7 days from receipt of the data and further repeats as necessary (ie, weekly until HBV DNA returns to <20,000 IU/mL).
- A post-treatment HBV DNA value of >2,000 IU/mL (but <20,000 IU/mL) should trigger a re-test within 14 days from receipt of the data and further repeats as necessary (ie, every other week until HBV DNA returns to <2,000 IU/mL).
- A post-treatment ALT value of >5x ULN should trigger re-testing of ALT, AST, ALP, total and direct bilirubin, INR, albumin, and HBV DNA on a weekly basis until ALT and AST levels have returned to <5x ULN.

After stopping NA treatment, participants should re-start NA treatment:

- Immediately with signs of decreasing liver function based on laboratory findings (eg, INR, direct bilirubin) or clinical assessment (eg, ascites, hepatic encephalopathy).
- Immediately with an HBV DNA value of >100,000 IU/mL (irrespective of confirmation and/or ALT increase).
- With confirmed post-treatment HBeAg seroreversion (HBeAg positive after it was negative at NA completion).
- With confirmed* post-treatment increases in HBV DNA >2,000 IU/mL and ALT >5x ULN.

- With confirmed* post-treatment increases in HBV DNA >20,000 IU/mL.

* *At least 4 weeks apart – frequency of visits as described above*

Note: Additional re-testing and/or earlier restarting of NA treatment is at the investigator's discretion, even if the above cut-offs are not yet met.

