1.1. Objectives and Endpoints

Objectives	Endpoints
Primary	

 To evaluate the efficacy in terms of HBsAg levels of the study intervention (i.e. JNJ-3989 + JNJ-6379^d + NA and PegIFN-α2a). 	
 Proportion of participants with a reduction of at least 2 log₁₀ IU/mL in HBsAg levels from baseline to Week 24 (end of study intervention [EOSI]).
Secondary	

 To evaluate the safety and tolerability of the study intervention. 	
 Safety and tolerability including but not limited to the proportion of participants with (serious) adverse events (S)AEs and abnormalities in clinical laboratory tests (including hematology, blood biochemistry, blood coagulation, urinalysis, urine chemistry, and renal biomarkers), 12-lead electrocardiograms (ECGs), vital signs, and ophthalmic and physical examinations throughout the study.

 To evaluate the efficacy of the study intervention at the end of the 24-week treatment period. 	
 Proportion of participants meeting the protocol-defined NA treatment completion criteria at EOSI.

 To evaluate the efficacy of the study intervention as measured by blood markers (such as HBsAg, HBeAg^a, HBV DNA, and alanine aminotransferase [ALT]) during the study intervention and follow-up (FU) period. 	
 Proportion of participants with HBeAg^a, HBsAg, HBV DNA, and ALT levels below/above different cut-offs. Proportion of participants with HBsAg and/or HBeAg^a seroconversion.

Objectives	Endpoints
	
 Change from baseline over time in HBsAg, HBeAg^a, and/or HBV DNA. Time to achieve HBsAg and/or HBeAg^a seroclearance/seroconversion, and/or HBV DNA < lower limit of quantification (LLOQ).

 To evaluate the frequency of virologic breakthrough^b during the 24-week treatment period, as well as during the FU period for participants who continue treatment with NA. 	
 Proportion of participants with virologic breakthrough^b.

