5.1.11. On-treatment and off-treatment periods

The on-treatment period begins with the first drug intake date and finishes with the maximum between:

- Last dose of NA + 2 days
- Last dose of PegIFN α 2a + 10 days,
- Last dose of JnJ-3989 + 28 days.

The off-treatment period stops if the NA re-treatment starts.

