5.4.2.1.14. Virologic Breakthrough

The count and proportion of participants (and associated 90% CI) who experience a virologic breakthrough and those who experience virologic breakthrough followed by on-treatment biochemical flare will be summarized, respectively, by analysis phase.

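### SAP 5.4.1.1.15 counts time on re-started NA as on-treatment, so the tail of an off-NA rebound can be reported as virologic breakthrough

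*SAP*

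**What the plan says.** **Breakthrough rule (SAP 5.4.1.1.15).** For anyone who has been below LLOQ on treatment, the event is a "confirmed on-treatment HBV DNA level >200 IU/mL in participants who had on-treatment HBV DNA level below the lower limit of quantification (LLOQ". Confirmation means that "the criterion should be fulfilled at 2 or more consecutive time points or at the last observed on-treatment time point". The period is set by: "On-treatment will be defined as the time period in which the participant receives any of the study interventions (including NA". NA belongs to the study intervention: the Protocol Synopsis says that, as of Amendment 3, this term "throughout the protocol, refers to JNJ-3989, NA, and pegylated interferon alpha-2a".

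**Objective (SAP 1.1, Protocol 3).** Breakthrough is to be evaluated over the 24-week treatment period, "as well as during the FU period for participants who continue treatment with NA".

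**Neighbouring rules.** SAP 5.4.1.1.16 closes an off-treatment virologic flare when NA is re-started, and treats the on-treatment counterpart of that flare as breakthrough. SAP 5.1.11 adds: "The off-treatment period stops if the NA re-treatment starts".

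**When NA is re-started (Protocol 6.7.1).** The first HBV DNA trigger reads "Immediately with an HBV DNA value of >100,000 IU/mL (irrespective of confirmation and/or ALT increase". The others are a confirmed value above 20,000 IU/mL, and a confirmed value above 2,000 IU/mL with ALT above 5x ULN. Loss of liver function and HBeAg seroreversion are also triggers.

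**Reporting.** Under SAP 5.4.2.1.14, participants "who experience a virologic breakthrough and those who experience virologic breakthrough followed by on-treatment biochemical flare will be summarized", by analysis phase. SAP 5.4.1.3.6 censors participants without an event at their last HBV DNA assessment at or before EOT.

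**The concern.** Breakthrough is meant to show loss of viral control while the participant is being treated. A rebound after a planned NA stop is a different event, and the SAP already reports it as an off-treatment flare and as NA re-treatment. Under the definition as written, the falling part of that rebound passes into the breakthrough count once NA is re-started. One episode can then appear as a virologic flare, a re-treatment and a breakthrough.

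The endpoint is a named secondary one and appears in every DRC package in SAP Table 10. True events may be few, so a handful of relabelled rebounds could make up most of the follow-up count. A reader could take the consequence of stopping NA for failure under treatment.

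**Working it through.** The plan gives no expected breakthrough or re-treatment rate, so there is no figure to reproduce for this endpoint. As a check on the interval method, Clopper-Pearson for 25/50 gives a 90% CI of 0.376-0.624, which matches SAP Table 1.

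**1. The chain in the text.**
- NA completion requires HBV DNA below LLOQ at Week 24 (SAP 5.4.1.1.1). Those who stop on the criteria therefore fall under the 200 IU/mL route.
- At restart the flare is closed and the off-treatment period ends.
- Time on any NA is on-treatment, and no clause in 5.4.1.1.15 or 5.4.2.1.14 excludes re-started NA.
- Post-restart values above 200 IU/mL therefore count if confirmed. The objective does not include them, because a participant who stops and re-starts has not continued NA.

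**2. How slow the decline must be.** The fall needed is log10(V/200), where V is HBV DNA at restart. With a linear log10 decline (assumption), both values stay above 200 IU/mL if the weekly rate is below that fall divided by the week of the second sample.

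| V (IU/mL) | Fall to 200 (log10) | Samples at weeks 4 and 8 (÷8) | Restart day and week 4 (÷4) | Weeks 1 and 2 (÷2) |
|---|---|---|---|---|
| 2,000 | 1.0 | 0.125 | 0.25 | 0.50 |
| 20,000 | 2.0 | 0.25 | 0.50 | 1.00 |
| 100,000 | 2.7 | 0.34 | 0.675 | 1.35 |

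**3. Benchmarks in the documents (Protocol 2.2.3.1, earlier Phase 2a study of JNJ-6379, participants not treated at screening).**
- HBeAg-positive, placebo + NA: 5.21/24 = 0.22 log10/week on average.
- HBeAg-negative: start at 4.89-5.40 log10, many below LLOQ from Week 4. With LLOQ 20 IU/mL (this SAP's value, assumed to apply there; arms mixed), (4.89 − 1.30)/4 = 0.90 to (5.40 − 1.30)/4 = 1.02 log10/week.

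These rates fall on both sides of most limits in the table.

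**4. Two examples from 100,001 IU/mL.**
- At 0.5 log10/week, re-tests at weeks 1 and 2 give 31,623 and 10,000: breakthrough. Visits at weeks 4 and 8 give 1,000 and 10: not confirmed.
- At 1.0 log10/week, weeks 1 and 2 give 10,000 and 1,000: breakthrough. If the second re-test comes 14 days after the first, week 3 gives 100: not confirmed.

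**5. Spread over assumptions.** Six restart values (2,001; 5,000; 20,001; 50,000; 100,001; 1,000,000 IU/mL) were crossed with 17 rates (0.20 to 1.00 in steps of 0.05), giving 102 combinations. Re-test spacing was taken from Protocol 6.7.1 and assumed to continue after restart. The two-value rule is met in:
- 13/102 (13%): 4-weekly visits, restart-day sample excluded;
- 45/102 (44%): 4-weekly visits, restart-day sample included;
- 54/102 (53%): re-tests used, restart-day sample excluded;
- 85/102 (83%): re-tests used, restart-day sample included.

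These are shares of an unweighted grid, not of participants. The clause on the last observed time point adds cases: one value suffices if the data cut-off or withdrawal follows soon after restart.

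**6. Time to first breakthrough.** SAP 5.4.1.3.6 limits censoring to EOT but does not limit events. SAP 5.5.1.5 labels Week 24 as EOT. On that reading, all event-free participants have left the risk set by Week 24. A single post-restart event then has a risk set of 1, and the Kaplan-Meier factor is 1 − 1/1 = 0, so estimated cumulative incidence jumps to 100%. This does not depend on the decline rate.

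**The case against.** The strongest reply is that the intended scope is clear: the objective names participants who continue NA, and the EOT censoring points the same way. But programmers work from 5.4.1.1.15, which states a wider rule, and the censoring text restricts only non-events.

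A reader might infer that nearly every re-treated participant would be labelled a breakthrough. The documents do not support that. Two consecutive values, or a last value, must exceed 200 IU/mL. The Schedule of Activities places sampling before NA intake, so the restart-day value is strictly pre-NA, although 5.4.1.1.15 does not exclude it. Protocol 6.7.1 does not say that intensified re-testing continues after restart. SAP 5.1.3 leaves open whether extra visits in a window would be used.

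A reader might also put a rate on the inflation. For example, 5/50 gives 10% (90% CI 4.0-19.9%), against 0/50 (0-5.8%). That needs an assumed number of re-treated participants, all of them relabelled, and no true breakthroughs; none of these is in the documents. The absence of breakthrough in the earlier study's NA-combination arms comes from Week 24 interim data and says nothing about follow-up after an NA stop.

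The limits on reach also stand. Planned NA stops occur at FU Week 2, so Treatment Period 1 and 2 results and the Week 12 and Week 16 data reviews are essentially untouched. Flare and breakthrough draw on different samples of the episode. Restarts are tabulated separately, so a careful reader could see the overlap.

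**Conclusion.** The rule is wrong as written. It admits post-restart samples that the objective leaves out, so the tail of an off-NA rebound can be reported as breakthrough. This reaches the follow-up-phase proportion, any overall proportion, time to first breakthrough, and breakthrough followed by on-treatment flare.

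The number of participants affected cannot be derived. It depends on how many re-start NA, at what level, how fast HBV DNA falls, and which samples are used. The 13% to 83% range shows only that the result is sensitive to those choices, under a linear log10 decline.

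The textual contradiction and the unequal treatment of events and censoring need no such assumptions. The study is exploratory, without formal tests, and the primary endpoint is unaffected, so this ranks below a must-fix.

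**What to change.** In SAP 5.4.1.1.15, state that for virologic breakthrough the on-treatment period runs from first dose to the first stop of NA, or to end of study for participants who never stop NA. A stop means a discontinuation, not missed doses. Exclude all samples from the NA-free period and after an NA restart, including the restart-day sample.

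Then:
- apply the same period to both events and censoring in 5.4.1.3.6, and to both summaries in 5.4.2.1.14;
- reconcile it with 5.1.11. If the last NA dose there can be a re-treatment dose, the general on-treatment period would also span the NA-free gap. State too whether that section's 2-day allowance applies here;
- report HBV DNA after restart only under the summary already planned in 5.4.2.1.10.

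The cost is a few sentences and one programming condition. Restarts are already identified from the NA administration CRF page (5.4.1.1.2), so no new data are needed. The downside is that loss of control during re-treatment no longer counts as breakthrough, but it stays visible in the post-restart HBV DNA summary.

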5.4.1.1.16. Flares

The criteria based on blood markers/lab tests for each of the flare types are defined as below.

1. Virologic flare is defined as follows:

Virologic flare will be assessed only for those participants who are off-treatment and had HBV DNA $< \text{LLOQ}$ at the last observed point on all study treatments.

The start of a confirmed virologic flare is defined as the first date of two consecutive visits with HBV DNA >200 IU/mL. The end date of the same confirmed virologic flare is defined as the first date when HBV DNA value returns to ≤ 200 IU/mL or the date of NA treatment restart, whichever comes first. Each virologic flare will be categorized based on the confirmed (i.e. two consecutive values) peak HBV DNA above any of the three thresholds within the start and end date of that flare as follows: 20,000 IU/mL, 2,000 IU/mL and 200 IU/mL.

- 1 (Yes) = confirmed** HBV DNA $>$ peak threshold.
- 0 (No) = at least one off-treatment HBV DNA measurement available and not meeting the criteria of confirmed HBV DNA $>$ peak threshold.
- 2 (Not applicable) = no off-treatment HBV DNA quantitative measurements available.

2. Off-treatment Biochemical flare is defined as follows:

The start date of a confirmed off-treatment biochemical flare is defined as the first date of two consecutive visits with ALT and/or AST $\geq 3x$ ULN and $\geq 3x$ nadir (i.e. lowest value observed up to the start of the flare) while the participant does not receive any of the study interventions. The end date of the same off-treatment biochemical flare is defined as the first date when there is a 50% reduction from the peak ALT and/or AST level & $< 3x$ ULN.

- 1 (Yes) = confirmed** ALT and/or AST $\geq 3x$ ULN and $\geq 3x$ nadir (i.e. lowest value observed up to the start of flare)
- 0 (No) = otherwise

3. On-treatment Biochemical flare is defined as follows:

The start date of a confirmed on-treatment biochemical flare is defined as the first date of two consecutive visits with ALT and/or AST $\geq 3x$ ULN and $\geq 3x$ nadir (i.e. lowest value observed up to the start of the flare) while the participant receives any of the study interventions. The end date of the same on-treatment biochemical flare is defined as the first date when there is a 50% reduction from the peak ALT and/or AST level & $< 3x$ ULN, regardless of stopping the study interventions.

- 1 (Yes) = confirmed** ALT and/or AST $\geq 3x$ ULN and $\geq 3x$ nadir (i.e. lowest value observed up to the start of flare)
- 0 (No) = otherwise

4. Clinical flare is defined as follows:

A clinical flare occurs either when a virologic flare and biochemical flare overlap in time or when a biochemical flare starts within 4 weeks following the end of a virologic flare. The start date of a clinical flare is defined as the minimum start date of the virologic flare and the biochemical flare. The end date of a clinical flare is defined as the maximum end date of the virologic flare and biochemical flare, i.e., the later date of HBV DNA returns to ≤ 200 IU/mL and 50% reduction from the peak ALT and/or AST level.

- 1 (Yes) = confirmed** HBV DNA $>$ peak threshold and confirmed** ALT and/or AST $\geq 3x$ ULN and confirmed** $\geq 3x$ nadir (i.e. lowest value during study participation).
- 0 (No) = otherwise

** Confirmed means that the criterion should be fulfilled at 2 or more consecutive time points or at the last observed time point.

The virologic and clinical flares will be assessed only off-treatment, while biochemical flares will be identified on-treatment and off-treatment. On-treatment virologic flares are described as virologic breakthrough in Section 5.4.1.1.15. On-treatment will be defined as the time period in which the participant receives any of the study interventions. Off-treatment will be defined as the period after stopping all study interventions (including NA).

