6.4.	Appendix 4 Protocol Deviations	71
6.5.	Appendix 5 Prior and Concomitant Medications	72
6.6.	Appendix 6 Medical History	73
6.7.	Appendix 7 Intervention Compliance	74
6.8.	Appendix 8 Adverse Events of Special Interest.....	75
6.9.	Appendix 10 Laboratory Toxicity Grading.....	80

7. REFERENCES..... 81

VERSION HISTORY

Document History	
Document	Date
Original SAP	30 June 2021
Amendment 1	15 October 2021
Amendment 2	18 May 2023

Amendment 2 (this document)

Overall rationale of this Amendment:

This is an administrative amendment that incorporates additional clarifications on endpoints, data handling rules, and updates to descriptive analyses that were previously documented in the Data Presentation Specifications.

Clarifications, Additions, Corrections		
Section Number and Name	Description of Change	Rationale
Section 5.1.9. Data Handling Rules	Revised ULOQ and Imputed Values data cutpoints for HBsAg, HBeAg and HBcrAg. Updated guidelines for the imputation of HBV DNA.	Improved language for clarity and precision.
Section 5.1.10. Main Groups for Analysis Section 5.3.2. Analysis Methods Section 5.4.2. Analysis Methods Section 5.5.2. Analysis Methods Section 5.6. Safety Analyses	Analyses will be focused on all subjects, and some analyses will be performed by group.	Change in the scope of the analysis.
Section 5.4.1.1.2 NA Re-Treatment Criteria During FU Section 5.4.2.1.2.1. NA Re-Treatment Criteria During FU	Removed NA re-treatment sub-criteria analysis.	NA re-treatment sub-criteria was not collected in CRF.

Clarifications, Additions, Corrections		
Section Number and Name	Description of Change	Rationale

Section 5.4.1.1.12. ALT Normalization
 
Section 5.4.2.1.8. HBeAg Seroconversion
 
Section 5.5.2.2.3. Anti-HBs Antibodies
	Removed an analysis.	
Majority of participants had ALT values within normal range at baseline.
 
HBeAg seroclearance is defined only for participants who were HBeAg positive at baseline.
 
Qualitative anti-HBs results are not collected.

Section 5.4.1.1.15. Flares	For on and off treatment biochemical flare definitions, nadir definition is updated to the lowest value observed up to the start of the flare.	The nadir definition was updated to include screening visit.
Section 5.4.2.1.10. Suppressed HBV DNA	Added two thresholds HBsAg and HBV DNA thresholds.	Additional analyses for HBsAg and HBV DNA thresholds were decided to be performed

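### The clinical-flare Yes line in SAP 5.4.1.1.16 uses a whole-study nadir while the biochemical-flare definitions use the nadir up to flare start, so the two can disagree in rare cases

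*SAP*

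**What the plan says.** SAP 5.4.1.1.16 defines four flare types, each with a narrative definition followed by a short numeric code (1 = Yes, 0 = No).

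- **Biochemical flares (items 2 and 3).** ALT and/or AST must reach at least 3x ULN and at least 3x nadir at two consecutive visits. The narratives define nadir as the "lowest value observed up to the start of the flare", and the Yes lines as the "lowest value observed up to the start of flare".
- **Clinical flare (item 4), narrative.** "A clinical flare occurs either when a virologic flare and biochemical flare overlap in time", or when the biochemical flare begins no more than 4 weeks after the virologic flare is over. Its start is the earlier of the two flares' start dates and its end is the later of their end dates.
- **Clinical flare (item 4), Yes line.** This restates the raw HBV DNA and ALT/AST criteria without naming the two flares, and gives nadir as the "lowest value during study participation".
- **Confirmation rule for the code lines.** "Confirmed means that the criterion should be fulfilled at 2 or more consecutive time points or at the last observed time point".
- **Closing paragraph.** Virologic and clinical flares are assessed only off treatment, that is, after all study interventions including NA have stopped.

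The SAP Amendment 2 change table reads: "For on and off treatment biochemical flare definitions, nadir definition is updated to the lowest value observed up to the start of the flare". It does not mention clinical flares, and its stated reason is "The nadir definition was updated to include screening visit". The protocol's Appendix 1 definition of ALT/AST nadir has the same wording as the clinical-flare Yes line.

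**The concern.** Item 4 gives two ALT/AST criteria for one endpoint. The narrative takes over the biochemical flare, and with it the nadir up to flare start. The Yes line uses a nadir with no time limit. When the analysis is run on a participant's complete record, that wording takes in values measured after the event.

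Two things follow if the Yes line is programmed as written. First, a participant can be coded as a clinical flare with no biochemical flare on record. The clinical flare's start and end, and the time to first clinical flare in SAP 5.4.1.3.7, then lack one of the dates they are built from, so the incidence table and the time-to-event analysis could count different people. Second, SAP Table 10 lists clinical flares at every data review, interim, primary and final analysis. A low value that arrives between two cut-offs could turn a past No into a Yes with no new event.

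**Working it through.** The plan states no figure to reproduce. The check compares the two rules directly.

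**Notation.** P is the lower of two consecutive ALT (or AST) values. N_pre is the lowest value up to flare start. N_all is the lowest value over the whole study. The HBV DNA part is taken as met.

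- Biochemical flare (items 2 and 3): P ≥ 3 × ULN and P ≥ 3 × N_pre.
- Enzyme part of the clinical-flare Yes line, read literally: P ≥ 3 × ULN and P ≥ 3 × N_all.

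**Direction.** N_all can never exceed N_pre, so P ≥ 3 × N_pre implies P ≥ 3 × N_all. The literal line can add clinical flares but cannot remove any.

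**When the rules differ.** This needs 3 × ULN ≤ P < 3 × N_pre together with P ≥ 3 × N_all. Hence N_pre > P/3 ≥ ULN, so every pre-flare value of that enzyme lies above ULN. It also needs N_all < N_pre, so a lower value must follow the event.

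**Upper limit for ALT.** Inclusion criterion A03 requires screening ALT below 2x ULN, and the Amendment 2 reason puts screening inside the nadir. So N_pre < 2 × ULN and P < 3 × 2 × ULN = 6 × ULN. Disagreement on ALT is therefore confined to P from 3x to below 6x ULN. The eligibility criteria give no numeric AST limit, so this bound is for ALT only.

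**Worked ALT series (U/L), assuming ULN = 40, so 3 × ULN = 120.** The two high values are 130 and 140 in each.

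| Series | N_pre | Ratios to N_pre | N_all | Ratios to N_all | Biochemical flare | Enzyme part of clinical Yes line |
|---|---|---|---|---|---|---|
| A: 52, 50, 55, 58, 130, 140, 70, 38, 36 | 50 | 2.60, 2.80 | 36 | 3.61, 3.89 | No | Met |
| B: 52, 50, 55, 58, 130, 140, 70, 50, 52 | 50 | 2.60, 2.80 | 50 | 2.60, 2.80 | No | Not met |
| C: 35, 30, 32, 31, 130, 140, 70, 25, 28 | 30 | 4.33, 4.67 | 25 | 5.20, 5.60 | Yes | Met |

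Series A shows the mismatch. Series B shows that it needs a lower value afterwards. Series C shows that a pre-flare nadir at or below ULN removes it.

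**Check of the algebra.** In 200,000 artificial nine-visit series (ULN 40, values between 15 and 300), 2,724 met the enzyme part of the clinical Yes line with no biochemical flare. None of these had a pre-flare nadir at or below ULN, and no series disagreed in the other direction. This confirms the conditions only. The series do not resemble trial data, and 2,724 says nothing about frequency in the trial.

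**After aligning the nadir.** Series A fails the clinical line too, because 2.60 and 2.80 are both below 3. The two codes then agree.

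**The case against.** The strongest reply is that a programmer should follow the narrative, which requires a biochemical flare. The Yes lines in this section are abbreviations: those for items 2 and 3 are identical although one flare is on treatment and the other off, and the line for item 1 does not repeat its own HBV DNA eligibility condition. The nadir wording is also the protocol's, where it guides real-time monitoring and can only mean the lowest value so far. Both points have weight. The first means that miscoding is possible but not certain. The second is weaker in a retrospective analysis, because the same SAP section now spells out the up-to-flare-start limit everywhere except in this line.

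A reader might infer more than the documents support:

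- **That clinical flares carry no timing condition, so any participant with both events months apart is affected.** The overlap or 4-week condition stands directly above the code, and the code lines are not written to stand alone.
- **That Amendment 2 set out to exclude post-flare values and was left unfinished.** Its stated reason is to bring in the screening visit, and its stated scope is biochemical flares only.
- **That a listed secondary endpoint is compromised.** The endpoint in SAP 1.1 names virologic and/or biochemical flares, and those definitions are unaffected.
- **That all of the approximately 50 participants are exposed to the problem.** Clinical flares are assessed only off treatment, and a virologic flare also requires HBV DNA below LLOQ at the last on-treatment point.

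**Conclusion.** The inconsistency is real and minor. The nadir in the clinical-flare Yes line differs from the one in every biochemical-flare definition and code line of the same section. Read literally, it allows a clinical flare without the biochemical flare that the narrative requires.

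All the conditions must hold in one person: off treatment, a confirmed virologic flare, all earlier values of that enzyme above ULN, a confirmed peak of at least 3x ULN but below 3x the pre-flare nadir, and a lower value later. The Amendment 2 change table says that most participants had ALT within the normal range at baseline, so few cases, if any, are to be expected. The documents give no count from which to estimate a frequency. Any error adds clinical flares and never hides one.

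The consequence is limited to a descriptive flare summary and the matching time-to-flare analysis. The primary endpoint is untouched. Monitoring and NA re-treatment follow separate protocol sections that do not use this code. The conclusion assumes that the Yes line is programmed literally on the full record. If the narrative is followed, no miscoding arises, but the SAP should not leave that choice to the programmer.

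**What to change.** In the clinical-flare Yes line of SAP 5.4.1.1.16, replace "lowest value during study participation" with "lowest value observed up to the start of the flare". Add that Yes also requires the overlap or within-4-weeks condition from the narrative of the same item. Keep the HBV DNA peak-threshold categories and the restriction to off-treatment assessment.

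A broader rewrite that simply pointed to the flares in items 1 to 3 would be less safe. Item 3 is the on-treatment flare, which would conflict with the off-treatment restriction, and the peak-threshold categories would be lost.

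The cost is one changed phrase and one added clause, plus a check that the derivation program matches. No data collection, visit or clinical rule changes.
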